6. INVESTIGATIONAL PLAN

6.1 VISIT SCHEDULE

Study procedures have to be completed according to the Flow Chart. All patients should adhere to the visit schedule as specified in the Flow Chart including time windows for rescheduling. Preferably the visits should be conducted in the morning.

If any visit has to be rescheduled, subsequent visits should follow the original visit schedule calculated from randomization (Visit 2). The trial medication kits contain sufficient medication to allow for these time windows.

6.2 DETAILS OF TRIAL PROCEDURES AT SELECTED VISITS

6.2.1 General requirements

The following requirements for the conduct of the assessments need to be followed:

- The MCCB should be done as the first efficacy assessment preferably in the morning (depending on the sleep cycle of the patient), followed by the VRFCAT, ToL and SCoRS.
- All other assessments can be completed per the convenience of patient and site at all respective visits.
- It is very important to have the MCCB done at approximately the same time of day for each individual patient throughout the trial. The MCCB assessments at Visit 6 and (e)EoT Visit must be started at approximately the same time of the day as MCCB assessment at Visit 2 (+/- 60 minutes). In case this cannot be adhered to, then the visit should be rescheduled within the allowed visit window.
- Assessment of each rating scale should preferentially be performed by the same rater for a given patient throughout the study period. However, for MCCB and VRFCAT, the consistency of time of day is more important than the consistency of the rater.

- To prevent bias on SCoRS rating, raters of SCoRS should remain blinded to the patient's performance on both MCCB and VRFCAT and MUST be different from the person administering MCCB and VRFCAT.
- During the MCCB assessments and throughout the visit, patients are allowed to take short breaks as needed, in the judgement of the rater/investigator.
- In case of patient experiences acute episode of schizophrenia (relapse), all efficacy assessments MUST be rescheduled (even if outside the visit window) until patient

Clinical Trial Protocol

Page 70 of 112

Proprietary confidential information © 2023 Boehringer Ingelheim International GmbH or one or more of its affiliated companies

stabilizes, per investigators judgment. All safety assessments including SSRS should be conducted, if possible.

- It is the responsibility of the PI at the site to ensure that all site staff members are properly trained on all trial procedures and training documentation is filed in the ISF.
 - o In addition, the site staff members who are administering scales must be trained and certified.
- Vital signs and ECG should always be measured before any blood samples are taken. For further details on how to collect ECG, please refer to section 5.2.4, for details on vital signs measurement, please refer to section 5.2.2.
- Any abnormal condition of clinical significance identified, during physical examination, vital signs, 12 lead ECG, laboratory assessment or any other medical assessment should be recorded as a baseline condition, if noted at screening, or as an AE if noted during treatment or follow up period, as applicable.
- Safety labs (including urinalysis) and/or urine drug screen, may be performed more frequently based on investigator discretion or if required locally.
- Patients do not have to come fasted for any trial visits.

Study partner requirements:

- The study partner should remain constant throughout the trial period, however in exceptional circumstances, a change of study partner will be allowed.
- Input from study partners will be required on the assessments indicated in the Flow Chart.
- In-person ratings are preferred whenever possible. However, if the study partner is not available for in-person ratings, telephone interview is acceptable. The telephone interview with the study partner must be conducted within the visits window indicated in the Flow Chart for which study partner input on SCoRS, required.

For study partners who also serve are also caregivers:

	Please refer to Appendix 10.2 for definition of	f study
partner vs. caregiver.		

• For caregiver assessments, in-person visit is preferred. However, if not possible, the caregiver may come on another day to fill-in the this should be as close to the visit as possible, preferably within the study visit window.

COVID-19 specific instructions:

During the COVID-19 pandemic, there might be situations when patients already in the study might not be able to come to the site for the scheduled visit. This might be due to restrictions set by authorities or by the investigator site/institution, because the patient is quarantined, or because of any patient specific situation that the investigator judges as being not safe for the patient to come to the site. For details on potential modifications of the trial conduct related to the COVID-19 pandemic, please refer to Appendix 10.3.

Page 71 of 112

Proprietary confidential information © 2023 Boehringer Ingelheim International GmbH or one or more of its affiliated companies

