Safety Laboratory tests ³	X		X		X		X		X	X^H	X	X	X		(X)		X		X	
PK Sample ⁴				X	X		X		X			X	X		X					
Bio-banking (optional) ⁵			X									X	X							
Speech sampling (optional) ⁶		X				X					X									
M.I.N.I. ⁷	X		X																	
In-/exclusion criteria	X		X																	
Randomization			X																	
AiCure training ⁸	X	(X)	X																	
AiCure review		X	X	X	X	X	X	X	X	X	X	X	X							
Contact IRT	X		X	X	X	X	X	X	X	X	X	X	X						X	
Duplicate patient check	X																			
(re)Dispense & administer trial drug at site ⁹			X	X	X	X	X	X	X	X	X									
IMP Compliance check				X	X	X	X	X	X	X	X	X	X							
Termination of trial drug												X	X							
MCCB	X		X				X					X	X							
VRFCAT	X		X				X					X	X							
PCRS & SCoRS ²⁰	X		X				X					X	X							
Tower of London	X		X									X	X							
		X	X				X				X	X	X		X		X		X	

Page 7 of 112

Proprietary confidential information © 2023 Boehringer Ingelheim International GmbH or one or more of its affiliated companies

FLOW CHART (con't)

Trial Periods and Procedures	Screening	g Period ¹				F	Rando	mized	Treat	ment l	Period	l			Sat	fety Follo	w-up Perio	od ¹⁸		End of Study
Visit	1	1a	2	3	4	5	6	7	8	9	10	EOT/11 ¹⁶	eEOT ¹⁷	Follow- up 1	Follow- up 2	Follow- up 3	Follow- up 4	Follow- up 5	Follow- up 6 ¹⁹	EOS
Weeks	Scree	ning	0	3	6	9	12	15	18	21	24	26	NA							
Days from first randomized treatment	-35 1		1	22	43	64	85	106	127	148	169	183	NA	EOT or eEOT + 7	EOT or eEOT +14	EOT or eEOT +17	EOT or eEOT +21	EOT or eEOT +24	EOT or eEOT + 28	
Clinic (on-site) visit	X	X	X	X	X	X	X	X	X	X	X	X	X		X		X		X	
Visit time window (days)	-35 to -28	-14 to -7	N/A	±3	±3	±3	±3	±3	±3	±3	±3	±3	NA	±1	±1	±1	±1	±1	+7	
PRECIS ¹⁰		X						X			X		X							
Adverse events ¹¹	X	X	X	X	X	X	X	X	X	X	X	X	X	X	X	X	X	X	X	
		X										X	X							
Concomitant therapy	X	X	X	X	X	X	X	X	X	X	X	X	X	X	X	X	X	X	X	
Substance use ¹²	X		X				X					X	X							
C-SSRS ²¹	X	X	X	X	X	X	X	X	X	X	X	X	X	X	X	X	X	X	X	
SAS/AIMS/BARS		X			X			X			X	X	X							
Physician withdrawal checklist ¹³											X		X	X	X	X	X	X	X	
Patient Participation Completion 14																				X
Duration in hours ¹⁵	7	3	6.5	1	2	2	4.5	2	2.5	1	3	6.5	7	0.5	2	0.5	3	0.5	3	

(X) Optional assessments at discretion of investigator

¹The screening period may take up to 35 days with 2 visits. At the second screening visit, urine drug screen may be repeated at discretion of investigators (X), if needed.

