
• Social Cognition: 3 items

The one additional item of the SCoRS falls within Language, which is not an MCCB domain.

The SCoRS rater integrates information from separate patient and study partner interviews to generate a total score. In addition, the patient, study partner and interviewer (rater) will provide a global rating score at each post-baseline visit and the interviewer (rater) will provide a change score at the eEoT visit.

Placebo Control Reminder Script (PCRS) [R20-4054]: The PCRS is a brief psychoeducational tool designed to mitigate placebo responses. A trained rater reads a brief passage about factors that have been linked to elevated placebo responses (e.g., misunderstandings about the purpose of a placebo treatment condition, unwarranted expectancies regarding treatment benefit) and encourages patients to attend to these factors. The patient and study partner are then asked to describe the content of the script in his/her own words. The procedure takes approximately three minutes to complete.

Virtual Reality Functional Capacity Assessment Tool (VRFCAT) will be used as an electronic Functional Capacity measure for this study [R20-0374]. The VRFCAT is a virtual reality shopping trip performed on a tablet. The task has several linked and sequential scenarios, including matching a recipe to the content of kitchen cabinets, preparing a shopping list, taking the correct bus, shopping efficiently, and catching the correct return bus. These tasks are performed in a fixed sequence. There are multiple forms of the VRFCAT and in this protocol different versions will be assigned according to the study visit. All data are collected through the computer or tablet.

Prior to the performance of the task, a brief tutorial version of the VRFCAT is administered with a short recipe. This tutorial needs to be administered to all patients, regardless of their statements regarding computer familiarity.

Once the task is launched it operates itself continuously until the end of the procedure. As with all electronic assessments, the tester will be required to remain vigilant in order to ensure that the patient is continuously engaged in the task. The task takes approximately 30 minutes to complete.

The VRFCAT was developed to improve clinical trials by detecting functionally meaningful improvements in patients' everyday lives. Data generated in this trial will support validation of this test as a functional outcome measure for future clinical trials.

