Tower of London (Executive Functions/Reasoning and Problem Solving):

Patients are shown two images presented on opposite sides of the tablet screen. Each image shows a different configuration of 3 coloured balls arranged on 3 pegs. The patient is required to accurately determine the total number of times the balls in one picture would have to be

Page 51 of 112

Proprietary confidential information © 2023 Boehringer Ingelheim International GmbH or one or more of its affiliated companies

moved in order to make the arrangement of balls identical to that of the other opposing picture, while employing the standard rules employed in tower tests (balls are moved one at a time and balls on top of other balls must be moved first). Eight alternative forms are available. The outcome measure is the number of correct responses. The administration time is about 7 minutes.

Patient Reported Experience of Cognitive Impairment in Schizophrenia (PRECIS) is a patient reported outcome (PRO) under development in accordance with FDA guidelines (2009) for recording patients' subjective experience of CIAS. The questionnaire contains 28 items and generally takes about 5-15 minutes to complete. The PRECIS asks the patient to assess their own subjective experience of CIAS over the past week, covering 6 domains: Memory (6 items), communication (4 items), self-control (3 items), executive function (4 items), attention (6 items), and sharp thinking (3 items). Two additional items assess the overall degree of bother associated with all domains. Questions are answered via a 5-category Likert scale, with higher scores corresponding to worse patient experience (1=not at all/not at all hard, 2=a little bit/a little bit hard, 3=somewhat/somewhat hard, 4=quite a bit/quite hard, 5=very much/very hard), e.g. "Overall, in the past week, remembering where I put things (for example, my keys, phone, glasses, or other items) was...". The Total Score is derived by calculating the simple average score of the first 26 items. Domain scores can be calculated as simple average of the items that fall into the respective domain. If there are more than 7 missing items out of the first 26, a total score should not be calculated. For number of missing items allowed for each domain scores see Table 5.1:2. Table 5.1:2 lists the 28 items of PRECIS, their corresponding domain, and the minimum number of non-missing items required for each domain.

Table 5.1: 2 PRECIS items, domains, and missing data allowance.

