6.2.3.1 Randomization (Visit 2)

- At the start of Visit 2, the investigator or designee should ensure that all Visit 1 and Visit 1a procedures have been successfully completed
- The MCCB should be performed before any other efficacy assessment.
- Study procedures for Visit 2 can be split into 2 sequential days, in which case:
 - o The MCCB and VRFCAT must be performed on the first day.
 - The remaining assessments can be done per the convenience of the patient and site, either on day 1 or day 2.
 - To reduce burden on the study partner, it is recommended to perform the and the SCoRS on the same day.
 - o In case of a split visit, the second day will be the day of first study drug intake.
- For patients who have signed the optional Biobanking consent form, biobanking (plasma and serum) samples should be collected before the intake of the first dose of study medication (refer to Section 5.5.1). The DNA sample may be collected at visit 2 or at another visit as long as the biobanking consent is has not been revoked.
- The MCCB overall T-score from the visit 1 (screening) is required to randomize the patient at visit 2.
 - In case the screening MCCB T-score is not available at visit 2, site may postpone this visit by maximum of 2 weeks.
- Patient eligibility must be confirmed before the patient is randomized in the IRT. Intake of the study medication must be done after the patient has completed all of the other visit 2 assessments.
- First intake of study medication will be done on site using the AiCure medication adherence monitoring app and under supervision by delegated trial staff.
- Two medication kits will be dispensed at visit 2. These kits will contain sufficient trial drug for 28 days (21 treatment days plus 7 days reserve). For further information refer to Section 4.1.4.
- At each clinic visit, patients should be reminded not to take study medication at home on the morning of the visit. At each visit, patient will take medication at the clinic using AiCure under supervision by trial staff.

6.2.3.2 Visit 3 to Visit 10

- blood samples will be collected during the treatment period as per the Flow chart.
 Refer to section 5.3 and Appendix 10.1 for more details.
- Patients should be instructed to bring all trial medication (used and unused kits/packaging including blisters) with them to these clinic visits.
- At each visit, the patient will receive a new supply of study medication, as allocated by the IRT system.

c33087946-03

Clinical Trial Protocol

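### The rule that keeps the SCoRS rater away from the performance tests omits Tower of London, so the text permits the rater to give and watch that test just before rating SCoRS

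*Protocol*

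**What the plan says.** Protocol Section 6.2.1 states the aim of the rule, "To prevent bias on SCoRS rating", and then sets two controls: "raters of SCoRS should remain blinded to the patient's performance on both MCCB and VRFCAT and MUST be different from the person administering MCCB". The first control concerns knowledge of performance; the second concerns who gives the test, and it covers VRFCAT too.

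The same section fixes the sequence of efficacy assessments. MCCB comes first, "followed by the VRFCAT, ToL and SCoRS". ToL is therefore the last thing the patient does before SCoRS.

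Section 5.1 introduces ToL as "Tower of London (Executive Functions/Reasoning and Problem Solving" and puts its duration at about 7 minutes on a tablet. It adds: "The outcome measure is the number of correct responses". Of SCoRS it says: "The SCoRS rater integrates information from separate patient and study partner interviews to generate a total score".

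SCoRS is a key secondary endpoint (Section 2.1.3), tested in the second family of the gatekeeping procedure. ToL is a secondary endpoint in the third family (Section 7.1).

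**The concern.** The rule's purpose is to let the SCoRS rating rest on the two interviews and not on what the rater has seen of the patient's test performance. ToL is a third performance test, yet neither control mentions it. A site that follows the protocol to the letter could have one person give MCCB and VRFCAT, and a second person give ToL and then conduct the SCoRS interviews. That second person would bring to the rating a source of information that is not part of the instrument.

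What is at stake is interpretation. SCoRS is one of the two measures meant to show that a cognitive gain reaches daily functioning. If the rater has just watched a cognitive test, a SCoRS difference becomes less separate from the performance measures, and so weaker evidence of function in its own right.

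**Working it through.** The plan gives no figure on this point, so the check is a comparison of texts.

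**Step 1: what the rule covers** (Sections 5.1 and 6.2.1, Flow Chart).

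| | MCCB | VRFCAT | ToL |
|---|---|---|---|
| Performance-based test | yes | yes | yes |
| Shown on a tablet | not stated for the battery | yes, runs by itself | yes |
| Place in the order before SCoRS | first | second | third, directly before |
| SCoRS rater blinded to performance | yes | yes | not stated |
| SCoRS rater must be another person | yes | yes | not stated |

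**Step 2: whether another text closes the gap.** Five places could do so.

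- Section 5.1 describes ToL and SCoRS without saying who gives ToL.
- The Flow Chart footnotes do not address it.
- Sections 6.2.3.1 to 6.2.3.4 deal with days and procedures, not with who tests.
- Inclusion criterion 8 and Appendix 10.2 separate professional study partners from test administration. That rule concerns study partners, not SCoRS raters.
- The SAP describes analysis only.

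None of them extends the rule to ToL.

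**Step 3: when the gap can operate.** The Flow Chart row "Tower of London" has marks at Visit 1, Visit 2, EOT/Visit 11 and eEOT. SCoRS is done at the same four visits and also at Visit 6. Hence:

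- Visit 2 (baseline) and EOT/Visit 11 (Week 26), the two time points of the SCoRS endpoint, are both exposed.
- Visit 1 matters less, but SAP Section 6.7 lets a Visit 1 SCoRS stand in as baseline when Visit 2 has none.
- Under SAP Table 6.7: 1, an eEOT assessment from Day 127 on can supply the Week 26 value.
- Visit 6 (Week 12) is not exposed, because ToL is not done there.

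**Step 4: how carry-over could reach the treatment comparison.** Let Δ_F be the arm difference SCoRS would show from the interviews alone, and Δ_T the arm difference in ToL performance. Let p be the share of patients whose SCoRS rater also gave ToL, and λ the weight such a rater gives to what was seen. With all terms in SD units and signed so that positive is better:

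Δ_SCoRS = Δ_F + p · λ · Δ_T

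Table 7.5: 1 of the protocol uses planning values for ToL of 0.2 and 0.275, so the added term would be 0.2 · p · λ to 0.275 · p · λ. The documents give neither p nor λ, so the term cannot be evaluated. Two things follow from its form. It is zero if no site combines the roles (p = 0). It is also zero if the drug does not change ToL performance (Δ_T = 0).

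**The case against.** **Nobody has planned this.** The protocol does not say who gives ToL. Section 6.2.1 requires scale administrators to be trained and certified, Section 8.7 points to vendor manuals for detail, and some text in Section 6.2.1 is blacked out. The roles may already be separated in practice. This stands: the finding is about what the visible text allows, not about what sites do.

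**ToL is a short tablet task, and the tester may not see which answers are right.** Part of this stands, because the documents do not say what the administrator sees. The reason for shielding is plainer for MCCB, which has scoring sheets. But the tablet format does not explain the omission. VRFCAT also runs by itself on a tablet and captures its own data, and the rule covers it. Section 5.1 expects the tester to stay watchful during electronic assessments in general, so some observation of the patient is to be expected.

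**Split visits.** A reader might infer a further fault, since only MCCB and VRFCAT are tied to the first day and, at Visit 2, "The remaining assessments can be done per the convenience of the patient and site, either on day 1 or day 2". ToL could then fall on different days at baseline and Week 26. The documents do not support treating this as a defect. The clause governs the day and does not expressly cancel the order in Section 6.2.1, to which Section 6.2.3 refers back. The freedom applies to both arms alike, and no harm to ToL is shown. A first-day requirement for ToL would be a preference and is not part of this point.

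**Conclusion.** The omission is real and worth closing, as a cheap improvement to an existing safeguard. The protocol's own reason for separating the SCoRS rater from MCCB and VRFCAT extends to ToL, and the text gives no reason for leaving it out. The possible consequence is a SCoRS rating less independent of test performance at the two visits that define the endpoint. This rests on three assumptions: that manuals and hidden text do not already separate the roles, that some sites combine them, and that the person giving ToL can form a view of how the patient did.

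Three stronger readings are tempting and not supported.

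- **Unblinding or a false-positive route.** Treatment stays double-blind. By Step 4, what is seen on ToL adds an arm difference only if ToL performance itself differs by arm.
- **A size of 15%.** Three of the 20 SCoRS items concern problem solving (3/20 = 15%), but Section 5.1 aligns those items with MCCB domains. The ratio describes shared subject matter, not bias.
- **All 586 patients affected.** That is a ceiling. It supposes that every site combines the roles and that every patient is assessed, while Section 7.5 itself allows 25% for missing data.

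The size of any effect cannot be derived from the documents.

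**What to change.** In protocol Section 6.2.1, extend both the blinding part and the different-person part of the rule to *MCCB, VRFCAT and ToL*, and state that the MCCB/VRFCAT tester gives ToL. No new role is needed, since that tester must already be someone other than the SCoRS rater; the added load on the tester is the 7 minutes or so that ToL takes. If a manual already separates the roles, the edit only brings the protocol into line with it.

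There is one real cost. Section 6.2.1 prefers the same rater for each scale throughout a patient's participation. Where one person now does both ToL and SCoRS, the change would alter the ToL administrator partway through for patients already enrolled. Either apply the rule to newly randomised patients only, or keep the SCoRS rater constant and change only who gives ToL.

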6.2.2 Screening period

Screening Period (Visit 1 and Visit 1a)

- A signed trial informed consent form must be obtained from the patient before either the patient or the study partner performs any study related procedure.
- A signed informed consent form must be obtained from the study partner before performing any study related procedure by the study partner.
- All consented patients must be recorded on the enrolment log and registered in the IRT system as a screened patient.
- Visit 1 may be performed over multiple days within the screening period. If visit 1 procedures are performed on multiple days, each individual assessment or procedure must not be conducted over 2 different days (for example, the entire MCCB must be performed on one day). All visit 1 procedures must be completed before completing visit 1a.
- **Duplicate patient check**: The patient IRT number and identifiers will be recorded on the VCT vendor portal to confirm that the patient is not participating in another clinical trial. Screening can only continue after Verified Clinical Trials provides confirmation. The investigator will receive email confirmation from the vendor that the patient is currently not participating in another trial in their database. Once email is received the site can continue screening.
- **Drug of abuse testing**: During screening, the investigator should highlight to patients the importance of not taking drugs of abuse during the study, and that a urine drug screen will be repeated periodically throughout the trial. Patients should also be informed that they cannot participate in the trial if they have a positive urine drug screen (see further the relevant exclusion criterion in Section 3.3.3).
- The MCCB scoring sheets must be sent to the vendor (VeraSci) as soon as possible. The Screening MCCB T-score is required for randomization via the IRT at visit 2.
- Please refer to the general requirements in Section 6.2.1.
- Eligibility Assessment:
 - Once all screening procedures are complete (including laboratory results are received), all data collected should be reviewed against the eligibility criteria.
 - O If the patient is eligible, the patient should be contacted to schedule next visit (Visit 2).
 - o If the patient is not eligible (i.e. if they are considered a screen failure), they must be registered as screen failure in IRT.
- **Rescreening:** Patients who fail screening may be re-screened once after a discussion between investigator and sponsor. Please see section 3.3 for further details regarding re-screening.

